11.3 Safety Review

An SMC will be appointed to oversee the safe conduct of the trial. A scheduled SMC meeting will be held after all subjects complete the trial to review safety data and advise on safety monitoring in future clinical trials of zoliflodacin. If criteria for halting the trial (as listed in [Section 9.5.1](#)) are met, an *ad hoc* SMC meeting will be held to review all available safety data and to make recommendations about the dosing of all further subjects in the trial. An independent unblinded statistician may present data in a closed session of an SMC meeting.

11.4 Final Analysis Plan

The ICH Guidance E9 (Statistical Principles for Clinical Trials) will be followed for all statistical content.²⁴ Summaries of frequencies and percentages will be presented for categorical data, and summary statistics such as minimum, median, mean, SD, and maximum values will be presented for continuous data. Details of safety, QTcF, other ECG interval measurements (QT, PR, QRS, RR and HR [based on RR measurements]), T-wave changes, ECG morphology, and PK and

PK/PD data analyses and presentations will be described in the Statistical Analysis Plan (SAP) and accompanying Tables, Listings, and Figures (TLF) templates. The SAP for safety and PK data will be prepared and finalized by the DCC before final data lock. The SAP for Holter ECG data will be prepared by IQVIA Cardiac Safety Services (CSS) and appended to the SAP. Analyses included in the clinical study report (CSR) will be performed by the DCC and CSS after final data lock. Any change from originally planned statistical analyses will be reported in the CSR.

11.4.1 Analysis Populations

All subjects who received at least one dose of study drug (zoliflodacin, placebo, or moxifloxacin) will be included in the safety population and analyzed as treated.

The PK analysis population will consist of all subjects who received zoliflodacin and have at least one quantifiable post-dosing drug concentration measured. The PK analysis subset will be based on the PK population, which includes all subjects who completed the PK part of the trial without any protocol violations that would likely affect the PK results and who have evaluable plasma concentration data for zoliflodacin from whom at least a subset of the designated PK parameters can be determined. If any subjects are found to be noncompliant with respect to dosing or have incomplete data, a decision to include them in the analysis will be made on a case-by-case basis.

The PD analysis population will include all subjects who provide evaluable Holter ECG data from at least one study treatment, without protocol deviations potentially impacting the ECG intervals. Exclusions from the PD analysis population due to protocol deviations will be decided before unblinding. Subjects must have at least one $\Delta\Delta\text{QTcF}$ value defined for inclusion in the PD analysis population.

The PD and PK analysis population will include all subjects who provide both evaluable Holter ECG and zoliflodacin PK data for the relevant study treatment. The PK/QTcF population will be the subset of subjects included in both the PD analysis population and the PK analysis population. Additionally, for the concentration-QTcF analysis, time-matched zoliflodacin concentrations corresponding to the ECG assessments will also be necessary.

11.4.2 Demographics and Baseline Characteristics

Subject demographics and baseline characteristics will be summarized. The number of subjects who enroll in the trial, and the number and percentage of subjects who complete each assessment, will be presented. The percentage of subjects who withdraw from the trial or discontinue the study drug, and reasons for withdrawal or discontinuation, will be summarized.

11.4.3 Safety Analysis

11.4.3.1 Adverse and Serious Adverse Events

AEs will be coded using the latest version of the Medical Dictionary for Regulatory Activities[®] (MedDRA). All AEs occurring after study drug dosing will be summarized using frequency counts and percentages. The following summaries will be presented for AEs and SAEs:

- Overall (i.e., regardless of severity or relationship to treatment);
- By severity grade (mild, moderate, or severe);
- By relationship to study drug;
- By MedDRA level hierarchy (system organ class [SOC], higher level group term [HLGT] and preferred term [PT]).

Unless otherwise specified, at each level of subject summarization in reporting the incidence of AEs, a subject will be counted once if the subject reported one or more AEs. If more than one occurrence of an AE is reported, the AE of the worst severity or the worst-case relationship assessment will be summarized.

11.4.3.2 Additional Safety Analyses

Descriptive summary statistics (mean, SD, median, minimum, and maximum) for clinical laboratory data, 12-lead standard ECG and Holter ECG parameters, and VS at admission and each applicable post-dosing visit, including changes from baseline values, will be calculated. If multiple baseline values are obtained, only the most recent value will be analyzed (with the exception of Holter ECG, see below). For change-from-screening summaries, subjects with an undefined change from screening, due to missing data, will be excluded. Clinical significance of abnormalities will be indicated in the listings.

11.4.4 PK Analysis

PK parameters will be estimated for zoliflodacin by noncompartmental methods using version 8.0 or higher of Phoenix[®] WinNonlin[®]. When evaluable, estimated PK parameters will include:

- $AUC_{(0-last)}$: Area under the concentration time-curve from time zero to the last concentration above the lower limit of quantitation
- $AUC_{(0-\infty)}$: Area under the concentration time-curve from time zero to infinity
- $AUC_{(0-t)}$: Area under the concentration time-curve from time zero to time t
- C_{max} : Maximum observed concentration
- T_{max} : Time of maximum observed concentration
- K_e : Elimination rate constant
- $t_{1/2}$: Terminal elimination half-life
- CL/F : Apparent oral clearance
- V_z/F : Apparent volume of distribution

Other PK parameters may be calculated, as appropriate.

The results will be listed by subject, and summarized with descriptive statistics including: n, mean, SD, coefficient of variation, median, minimum, maximum, geometric mean, and geometric SD.

Graphical presentations of concentration vs. time profiles will be provided for zoliflodacin and will include individual subject and mean concentration profiles. Semi-log concentration profiles will be provided for individual subjects.

11.4.5 Missing Values and Outliers

All attempts will be made to collect all data per protocol. No imputation will be performed for missing values. Outliers will not be excluded from the primary analyses. Outliers identified during the PK analysis will be discussed in the analysis report.

11.4.6 Analysis of Continuous ECG Parameters (Pharmacodynamics)

11.4.6.1 ECG Analysis and Interpretation

The $\Delta\Delta\text{QTcF}$, calculated as differences between time-matched mean change-from-baseline QTcF values for active treatment relative to placebo, will be evaluated to quantify the QTcF prolongation of the active treatments. The median of the three Holter ECG QTcF interval measurements at 45, 30, and 15 min before each dosing will be regarded as baseline for the respective period.

QTcF corrections will be calculated using Fridericia's formula:

- $\text{QTcF} = \text{QT} / \text{RR}^{0.33}$

The primary variable will be the change-from-baseline QTcF (ΔQTcF). Other endpoints to be evaluated include HR (bpm; calculated from RR interval measurements), PR (msec), QRS (msec), RR (msec), and cardiac abnormalities (morphologies, rhythm, and conduction).

All statistical analyses and reporting of digital ECG data will be conducted on the mean of the replicate intervals within a timepoint. Descriptive statistics including two-sided 90% CI will be generated for observed, change-from-baseline, and time-matched placebo-corrected change-from-baseline ECG intervals.

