8.3 Special Procedures and Assays

8.3.1 Continuous 24-h ECG Monitoring (Holter ECG Monitoring)

ECGs for assessment of the primary endpoint will be obtained digitally during all four dosing periods using a continuous 12-lead Holter ECG digital recorder system. The continuous ECG recording will be started approximately 1 h before dosing on Day 1 of all dosing periods and will continue until 24 h after dosing (i.e., in the morning of Day 2). Three replicate ECG recordings will be extracted at the following timepoints in each dosing period: 45, 30, and 15 min before dosing (baseline) and 0.5, 1, 2, 3, 4, 6, 8, 12, and 24 h after dosing for a total of 12 timepoints per subject per dosing period. The subject will be in a supine position for at least 10 min before recording an ECG and 5 min after the nominal timepoint for the ECG extractions from the Holter monitors. These timepoints will correspond to PK blood sampling for each dosing period, but ECGs will be obtained before the measurement of VS and collection of blood samples, to avoid the effect of stress on the ECG. The mean of pre-dose ECGs extracted on Day 1 of each dosing period will be used as baseline reference for results obtained after dosing.

ECGs will be extracted from the Holter recordings over a 5-min period and used to measure ECG intervals. Digital QT, QTcF, PR, QRS, and RR intervals and HR will be determined by the Core ECG Lab. Digital ECGs will be read in accordance with the principles outlined in ICH E14 Guidance for TQT studies.¹⁶

The 12-lead Holter and ECG equipment will be supplied and supported by the VACR Phase 1 CTU. All ECG data will be collected using a continuous 12-lead ECG digital recorder. The continuous 12-lead digital ECG data will be stored onto secure digital memory cards. ECGs to be analyzed will be collected at pre-determined timepoints (as indicated above and in [Appendix A: Schedule of Study Procedures and Evaluations](#)) and will be read centrally by IQVIA Cardiac Safety Services.

The following principles will be followed in the IQVIA Cardiac Safety Services core laboratory:

- Each extracted ECG will be analyzed by the cardiologist who will be blinded to subject identifiers, time, and treatment.
- Electrocardiograms will be analyzed for PR, QRS, RR, and QT intervals using semi-automated measurements and for morphological abnormalities including T and U waves manually by experienced cardiologists.

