14. TECHNICAL DETAILS

SAS version 9.4 or above or R versions 3.2 or above will be used to generate tables, figures, and listings. PK parameters will be estimated through a NCA using Phoenix[®] WinNonlin[®] version 8.0 or later (Pharsight Corporation, Cary, NC).

**15. SUMMARY OF CHANGES IN THE CONDUCT OF THE STUDY OR
PLANNED ANALYSES**

None to report.

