5.5. PHARMACOKINETIC-QTcF ANALYSIS.....	21
5.5.1. Hysteresis effect check	21
5.5.2. Testing for linearity:	22
5.5.3. Model selection:	22
5.6. GRAPHICAL ANALYSIS.....	23
6. REFERENCES	23

Modification History

Unique Identifier for this Version	Date of the Document Version	Section number and text from previous version	Section number and text in new version
Draft 01	16JUL2018	Not Applicable – First Version	
Draft 02	13AUG2018	1. Inserting throughout text the appropriate references to TLFs #s	Wherever applicable in this document
		2. Reviewer from Sponsor added	Signature page
		3. Review abbreviations in Final and delete/add as needed.	Updated the abbreviation list
		4. In the entire document wherever applicable, when the abbreviation is used for the first time, it is now spelled out.	As per review comments
		5. Global comment ‘Remove hyphen in DMID-16-0110’	Updated wherever applicable in this document
		6. Global comment ‘Postdose’ added hyphen ‘post-dose’ throughout the document	Updated wherever applicable in this document as per reviewer’s comment
		7. Section 2.2 – Study Outcome measures	Updated as per study protocol text
		8. Section 3 – Study design	Updated as per study protocol text and review comments
		9. Section 4 – Reworded ‘Analysis Set’ to ‘Analysis Population’	As per review comments
		10. Section 5 – reworded ‘average’ to ‘mean’	As per review comments

		11. Added 'Calculated from RR' in parenthesis to Heart rate in Section 5 and in the rest of the document	As per review comments
		12. Added analysis for RR	As per review comments
		13. Added analysis for QTcB	As per sponsor discussion and as per ICH E14 guidance.
		14. Deleted 'groups' where 'Treatment groups' appeared in the text	As per review comments
		15. Section 5 onwards – changed 2-sided 90% confidence intervals to one-sided 95% confidence intervals	As per review comments
		16. Section 5.3 – Added Baseline to be determined for each period separately. reworded 'average' to 'mean'	As per review comments
		17. Section 5.3 – Table 3 – Added Day 2 to Day1 Hour 24 timepoint	As per review comments
		18. Section 5.4.1 – Added QTcB for categorical outlier analysis.	As per sponsor discussion and as per ICH E14 guidance.
		19. Section 5.4.2 – Clarified the baseline considered for treatment emergent morphological abnormalities	Based on review comments
		20. Section 5.5 title changed from 'Concentration-QTcF analysis' to 'Pharmacokinetic – QTcF Analysis'	As per review comments

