3.1. Overview of Holter ECG Data Collection in the Study

ECGs will be recorded during all four dosing periods using high resolution (1000 Hz) 12-lead Holter ECG equipment.

The continuous ECG recording will start approximately 1 h before dosing on Day 1 of all dosing periods and continue until 24 h after dosing (i.e., in the morning of Day 2). Three replicate ECG recordings will be extracted at the following timepoints in each dosing period: 45, 30, and 15 minutes before dosing (baseline) and 0.5, 1, 2, 3, 4, 6, 8, 12, and 24 h after dosing for a total of 12 timepoints per subject per dosing period. The subject will be in a supine position for at least 10 minutes before recording an ECG at the nominal timepoint for the ECG extractions from the Holter monitors. These timepoints are to correspond to the PK blood sampling timepoints for each dosing period with ECGs being obtained before the measurement of VS and collection of blood samples, to avoid the effect of stress on the ECG. The mean of pre-dose ECGs extracted on Day 1 of each dosing period will be used as the baseline reference for comparison with post-dose ECGs.

The primary objective and primary outcome measure in this study is based on QTcF values. However, the ICH-E14 guidance acknowledges that all formulae make assumptions about the nature of the QT-HR relationship that may not apply to those with disease or taking drugs. The ICH-E14 guidance, therefore, suggests that uncorrected QT and RR interval data, HR data, as well as QT interval data corrected using Bazett's (QTcB) and Fridericia's (QTcF) corrections should be submitted in all applications, in addition to QT interval data corrected using any other formulae.² Thus, this analysis plan also includes statistical analysis of QTcF, QTcB, HR (calculated from RR), RR interval, QT interval, PR interval and the QRS duration.

4. Analysis Populations related to Expert ECG Report

Holter ECG Analysis Population: The Holter ECG Analysis Population will include all subjects who have received at least one dose of zoliflodacin, moxifloxacin, or placebo, treatment, without protocol deviations potentially impacting the ECG intervals and have baseline ECGs and at least one post-dose ECG assessment.

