5.3. Study Holter ECG Timepoints

At each study timepoint, the mean value of an ECG parameter from all available replicate ECGs recorded at that timepoint (maximum of 3 replicates) for an individual subject will be considered as the value of the ECG parameter at the nominal timepoint for the subject.

Baseline: Baseline will be determined separately for each dosing period. Mean of triplicate ECGs recorded at 3 pre-dose assessments (mean of 9 ECGs) on Day 1 (i.e. D1PRE45MIN, D1PRE30MIN and D1PRE15MIN) of each treatment period will be considered as baseline for the corresponding treatment period.

Holter ECG analysis timepoints for the study are as follows:

Table 3: Holter ECG Timepoints as per Visit code poster and Visit codes used in ECG database

No.	Timepoints as per Visit code poster	Visit Codes in ECG database
1	Period 1 Day 1 Predose 45 minutes	P1D1PRE45MIN
2	Period 1 Day 1 Predose 30 minutes	P1D1PRE30MIN
3	Period 1 Day 1 Predose 15 minutes	P1D1PRE15MIN
4	Period 1 Day 1 Post dose 0.5 hours	P1D1H0.5
5	Period 1 Day 1 Post dose 1 hour	P1D1H1
6	Period 1 Day 1 Post dose 2 hour	P1D1H2
7	Period 1 Day 1 Post dose 3 hour	P1D1H3
8	Period 1 Day 1 Post dose 4 hour	P1D1H4
9	Period 1 Day 1 Post dose 6 hour	P1D1H6

No.	Timepoints as per Visit code poster	Visit Codes in ECG database
10	Period 1 Day 1 Post dose 8 hour	P1D1H8
11	Period 1 Day 1 Post dose 12 hour	P1D1H12
12	Period 1 Day 1 Post dose 24 hour (Day 2)	P1D1H24
13	Period 2 Day 1 Predose 45 minutes	P2D1PRE45MIN
14	Period 2 Day 1 Predose 30 minutes	P2D1PRE30MIN
15	Period 2 Day 1 Predose 15 minutes	P2D1PRE15MIN
16	Period 2 Day 1 Post dose 0.5 hours	P2D1H0.5
17	Period 2 Day 1 Post dose 1 hour	P2D1H1
18	Period 2 Day 1 Post dose 2 hour	P2D1H2
19	Period 2 Day 1 Post dose 3 hour	P2D1H3
20	Period 2 Day 1 Post dose 4 hour	P2D1H4
21	Period 2 Day 1 Post dose 6 hour	P2D1H6
22	Period 2 Day 1 Post dose 8 hour	P2D1H8
23	Period 2 Day 1 Post dose 12 hour	P2D1H12
24	Period 2 Day 1 Post dose 24 hour (Day 2)	P2D1H24
25	Period 3 Day 1 Predose 45 minutes	P3D1PRE45MIN
26	Period 3 Day 1 Predose 30 minutes	P3D1PRE30MIN
27	Period 3 Day 1 Predose 15 minutes	P3D1PRE15MIN
28	Period 3 Day 1 Post dose 0.5 hours	P3D1H0.5
29	Period 3 Day 1 Post dose 1 hour	P3D1H1
30	Period 3 Day 1 Post dose 2 hour	P3D1H2
31	Period 3 Day 1 Post dose 3 hour	P3D1H3
32	Period 3 Day 1 Post dose 4 hour	P3D1H4
33	Period 3 Day 1 Post dose 6 hour	P3D1H6
34	Period 3 Day 1 Post dose 8 hour	P3D1H8
35	Period 3 Day 1 Post dose 12 hour	P3D1H12

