5.4.1. Categorical analysis

Categorical outlier analysis will supplement the central tendency analysis by determining if there were individual subjects who had an exaggerated effect on any ECG interval that were not revealed in a mean change from baseline central tendency analysis.

ECG parameter values from individual post-dose replicate ECGs at each timepoint (not mean or median of all replicates) will be considered separately for categorical outlier analysis.

Results of categorical outlier analysis will be presented as number and percentage of subjects in each treatment. Results will be tabulated by individual treatment. If a subject has more than one categorical outlier value for a parameter at a timepoint, then the subject will be counted only

once for that timepoint. Statistical tests for comparison between treatment arms will not be performed.

For outlier analysis, the baseline value for each participant is defined as mean of 3 pre-dose assessments (9 ECGs) on Day 1 (i.e. D1PRE45MIN, D1PRE30MIN and D1PRE15MIN) of the corresponding treatment period.

ECG parameters namely QT/QTc will be flagged as normal, abnormal insignificant or significant, based on the pre-approved study specific ECG abnormality criteria based on ICH E14 guidance.²

The categorical outlier values for QTcF, QTcB, HR, PR, and QRS parameters (**Refer to DMID 16-0110_ECG_Table shells: Table 9; DMID 16-0110_ECG_Listing shells: Listings 8 to 13**) for the individual subjects in each dose cohort will be summarized as follows:

1. QTcF and QTcB will be categorized using the following study-specific criteria:
 - QTc >450 msec to 480 msec
 - QTc >480 msec to 500 msec
 - QTc >500 msec
 - QTc increase from baseline ≥ 30 msec to <60 msec
 - QTc increase from baseline ≥ 60 msec
2. Uncorrected QT will be categorized for >500 msec.
3. Categorical outliers for HR (calculated from RR) will be categorized based on the following criteria:
 - HR change-from-baseline >25% decrease resulting in HR <50 bpm
 - HR change-from-baseline >25% increase resulting in HR >100 bpm
4. Categorical outliers for PR and QRS parameters will be categorized for the following criteria:
 - PR change-from-baseline >25% resulting in PR >200 msec
 - QRS change-from-baseline >25% resulting in QRS >120 msec

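### Does it matter that the protocol defines the Holter QTcF baseline once as a median and elsewhere as a mean?

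*Protocol*

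**What the plan says.** Protocol 11.4.6.1, the statistical section on ECG analysis, states: "The median of the three Holter ECG QTcF interval measurements at 45, 30, and 15 min before each dosing will be regarded as baseline". The same section adds that replicates within a timepoint are averaged.

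Protocol 8.3.1, which describes Holter monitoring, states: "The mean of pre-dose ECGs extracted on Day 1 of each dosing period will be used as baseline reference".

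The ECG SAP (Appendix 4 of the SAP) uses the mean throughout:

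- Section 3.1: "The mean of pre-dose ECGs extracted on Day 1 of each dosing period will be used as the baseline reference".
- Section 5.3: "Mean of triplicate ECGs recorded at 3 pre-dose assessments (mean of 9 ECGs) on Day 1".
- Section 5.4, which derives the variable for the primary analysis, subtracts the mean of the baseline replicates from the post-dose mean.
- Section 5.4.1: "For outlier analysis, the baseline value for each participant is defined as mean of 3 pre-dose assessments (9 ECGs) on Day 1".

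On responsibility, Protocol 11.4 leaves the details of the QTcF analysis to the SAP and says: "The SAP for Holter ECG data will be prepared by IQVIA Cardiac Safety Services (CSS) and appended to the SAP". It also requires departures from the planned analysis to be reported in the CSR. Section 15 of the main SAP, on changes, reads: "None to report".

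**The concern.** Baseline is part of every ΔQTcF and ΔΔQTcF value, it is a covariate in the primary mixed model, and it sets the 30 and 60 msec outlier categories. Two definitions of it could move all 18 confidence bounds on which the negative conclusion rests.

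The rule about averaging replicates does not resolve the matter. It applies within a timepoint, whereas the median combines three different timepoints. Both can be obeyed together, giving a median of three triplicate means, which is not a mean of nine ECGs. For example, timepoint values of 400, 402 and 415 msec have a median of 402 and a mean of (400 + 402 + 415)/3 = 405.7 msec.

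No text gives an order of precedence, and no change is declared. An analyst working only from Protocol 11.4.6.1 would therefore obtain different individual values from one working from the ECG SAP, for a primary endpoint that is judged pass or fail.

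**Working it through.** **Which rule will be used.** Protocol 11.4 assigns the Holter analysis plan to the ECG core laboratory and has the data coordinating center and that laboratory run the analyses. Their document says mean in all four places listed above, including the primary derivation in 5.4. The protocol also says mean in 8.3.1, so the ECG SAP adopts one of two definitions already in the protocol. The median wording covers QTcF only. For PR, QRS, RR and heart rate the mean is the sole definition and there is no conflict.

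**Inputs.** From Protocol 11.2: n = 56 evaluable, SD of ΔΔQTcF = 7 msec, true effect 5 msec, stated power at least 84%. From Protocol 11.4.6.2: margin 10 msec, one-sided 95% bounds, 18 of them. My assumptions: independent normal timepoint errors, and SD 7 applying under the mean rule. The ratio r of pre-dose to post-dose error SD is not in the documents, so I give a range.

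**The plan's own figure.** Power for one bound = Φ(5/(7/√56) − 1.645) = Φ(5.345 − 1.645) = Φ(3.70) = 99.99%. This satisfies the stated minimum of 84%, although it is far above it.

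**Precision of the two baselines.** In units of the pre-dose error variance:

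- Median of three: 1 − √3/π = 0.4487.
- Mean of three: 1/3 = 0.3333.
- Their difference: 0.4487 − 0.3333 = 0.1154.

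Ratio of standard errors of ΔΔQTcF, median to mean = √[(1 + 0.4487r²)/(1 + r²/3)]:

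- r = 1: √(1.4487/1.3333) = 1.042.
- r = 2: √(2.7948/2.3333) = 1.094.
- r very large: √(0.4487/0.3333) = 1.160.

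**Effect on one upper bound.** The half-width under the mean is 1.673 × 7/√56 = 1.565 msec. The median adds:

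- r = 1: 1.565 × 0.042 = 0.07 msec.
- r = 2: 1.565 × 0.094 = 0.15 msec.
- Limit: 1.565 × 0.160 = 0.25 msec.

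The estimated mean ΔΔQTcF itself would differ between the rules by a random amount with SD 0.27 msec (r = 1) or 0.42 msec (r = 2), centered on zero when errors are symmetric.

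**Effect on the decision.** Simulated with paired t bounds and r = 1:

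| Setting | Rules disagree | Pass, mean | Pass, median |
|---|---|---|---|
| 1 bound, 5 msec, SD 7 | 0.03% | 99.99% | 99.97% |
| 18 bounds, 5 msec, SD 7 | 0.3% | 99.8% | 99.5% |
| 18 bounds, 6 msec, SD 7 | 5.7% | 92.8% | 89.3% |
| 18 bounds, 5 msec, SD 9.9 | 11% | 77.5% | 71.6% |

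The first two rows use the plan's effect and SD. The 18-bound rows put the same true effect at every timepoint and both doses, which is a worst case. The SD of 9.9 (7 × √2) is a sensitivity value that is not in the documents. With an assumed effect peaking at 2 h for 4 g, and half as large for 2 g, the 18-bound disagreement falls to about 0.05%, 0.6% and 2.2% in the same order.

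**The case for a change.** The strongest opposing case concerns prespecification more than size. The primary variable should have one definition before unblinding. Protocol 11.4.3.2 sends the reader forward for the Holter baseline, and what follows is the median, so the median can fairly be read as the protocol's analysis definition. The main SAP expands on the protocol without claiming to override it. Repair would take one sentence. Near the margin, or with a larger SD, the rules would disagree more often, as the lower rows of the table show.

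Part of this stands: the two protocol sections do contradict each other, and a reader may ask why. The evidence for an undeclared departure is weaker than it looks.

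- The nil entry in main SAP Section 15 belongs to a text whose stated scope is safety and PK, although the ECG SAP is appended to it, so this point is arguable.
- The duty to report changes falls on the CSR, a later document.
- The ECG SAP modification history, which includes "Added Baseline to be determined for each period separately", records edits between its own drafts. Its silence on the median shows nothing about the protocol.
- The ECG SAP cites protocol Version 1.0 and the main SAP cites v3.0, but the documents do not show what Version 1.0 said about baseline, so the gap carries no weight.

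The disagreement rates compare two analyses of which only one is planned. They would describe a risk only if someone might actually program the median.

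**Conclusion.** This is an internal inconsistency in the protocol, limited to QTcF, and no change to the plan follows. The document that governs the Holter analysis gives one definition, repeats it, and uses the more precise of the two. Making the protocol agree would leave every planned value unchanged.

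Had the median been used, the cost at the plan's own inputs would have been about 0.07 msec on an upper bound (0.15 msec if the pre-dose SD were double the post-dose SD). The decision would have differed in about 0.03% of trials for one bound and 0.3% for 18. These figures assume independent normal errors and paired t bounds. The baseline covariate in the mixed model may reduce them. Absence of bias rests on symmetric pre-dose errors. Study halting uses standard 12-lead ECGs (Protocol 9.5.1.1) and the safety baselines are defined separately (main SAP 3.3), so neither is affected.
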